2. INTRODUCTION

2.1. Study rationale

In the currently marketed Ventolin Evohaler, micronized particles of salbutamol are suspended in propellant HFA-134a [[VENTOLIN EVOHALER](#), 2023]. However, HFA-134a has significant GWP and hence its use in medicine and other applications is being phased out under mounting environmental pressure to replace it with a low carbon footprint alternative such as salbutamol HFA-152a (test).

GSK is seeking to develop a sustainable version of the current Ventolin Evohaler to address global climate change. This study will evaluate the pharmacokinetics of salbutamol administered via MDIs containing propellants HFA-152a (test) and HFA-134a (reference). Hereafter, salbutamol administered via MDIs containing propellant HFA-152a (test) will be referred to as salbutamol HFA-152a and salbutamol administered via MDIs containing propellant HFA-134a (reference) will be referred to as salbutamol HFA-134a.

2.2. Background

Approximately 339 million people currently suffer from asthma, and it is the most common noncommunicable disease among children [[GINA](#), 2023]. Asthma requires medical assessment and care when it occurs on either a persistent, or intermittent but frequently recurring basis. Exacerbations of asthma are episodes characterized by a progressive increase in symptoms of shortness of breath, cough, wheezing, or chest tightness and a progressive decrease in lung function, such that they represent a change from the patient's usual status that is sufficient to require a change in treatment [[GINA](#), 2023]. Severe exacerbations are potentially life-threatening and their treatment requires close medical supervision [[GINA](#), 2023].

Pharmacotherapy for asthma follows a stepwise process determined by symptoms and disease severity. The most common treatment options are short- and long-acting bronchodilators, corticosteroid anti-inflammatory agents, and combination products containing both bronchodilators and corticosteroids. Biological agents are also available for more severe disease in patients with eosinophilic asthma. Short-acting reliever medications such as salbutamol sulfate are a cornerstone of asthma therapy for as-needed relief of breakthrough symptoms, including worsening asthma or exacerbations [[GINA](#), 2023]. Salbutamol sulfate, the active ingredient in Ventolin Evohaler (HFA-134a) is approved in over 130 countries.

Salbutamol sulfate is a selective β_2 -adrenergic receptor agonist that acts on bronchial smooth muscle providing short-acting (4 to 6 hour) bronchodilation with a fast onset (within 5 minutes) and is suitable for the relief and prevention of asthma symptoms and reversible airway obstruction.

[figure not shown]
Inhaled salbutamol has been approved for human use since 1968 initially as an MDI containing CFC propellants. These propellants were later replaced with propellant HFA-134a due to international treaties phasing out CFC production arising from environmental

concern. GSK is developing a sustainable version of its Ventolin Evohaler using an alternative new propellant, HFA-152a which will replace the current propellant, HFA-134a. The chemical structures of the 2 propellants are presented in [Figure 3](#).

Figure 3 Chemical structures of HFA-134a and HFA-152a

[figure not shown]
Propellant HFA-134a

1,1,1,2-tetrafluoroethane

[figure not shown]
Propellant HFA-152a

1,1-difluoroethane

Salbutamol HFA-152a will be developed as a replacement product for the current Ventolin Evohaler (HFA-134a) with the same indications and posology. HFA-152a is an MDI delivering 100 µg of salbutamol (as salbutamol sulfate) per dose; 200 doses per device. Salbutamol has a duration of action of 4 to 6 hours with administration of up to 2 inhalations (200 µg total) not exceeding 4 times daily.

CCI

The maximum recommended total daily dose of salbutamol for chronic use delivered via the Ventolin MDI is 800 µg. This dose requires 8 inhalations (800 µg salbutamol). The exposure to HFA-152a (8x63 µL) is estimated to be 454 µg/day (6.87 µmol/day). This is well below the exposures of HFA-152 shown to have no adverse effects in humans.

2.3. Benefit/risk assessment

Detailed information about the known and expected benefits and risks and reasonably expected AEs of salbutamol delivered via MDI may be found in the patient information, package insert and SmPC. There is no added benefit expected for the healthy participants. A risk assessment has been presented in Section [2.3.1](#).

2.3.1. Risk assessment

Potential Risk of Clinical Significance	Summary of Data/Rationale for Risk	Mitigation Strategy
Study Intervention		
Participants will be instructed to administer 200 µg or 800 µg of salbutamol. There is a potential risk that the HFA-152a propellant delivers a higher effective dose of salbutamol compared to the reference Ventolin Evohaler	
Hypokalemia: β-adrenergic agonist medicines may produce significant hypokalemia in some patients, possibly through intracellular shunting, which has the potential to produce adverse cardiovascular effects. The decrease in serum potassium is usually transient, not requiring supplementation.
 
Hyperglycemia: β-adrenergic agonist medicines may produce a transient rise in serum glucose which is not expected to be clinically significant with inhalational administration. However, large doses of intravenous salbutamol have been reported to aggravate pre-existing diabetes mellitus and ketoacidosis.
 
Cardiovascular effects: β-adrenergic agonist medicines may produce clinically significant cardiovascular effects in some patients such as changes in pulse rate or blood pressure. In addition, β-agonists have been reported to produce ECG changes, such as flattening of the T wave, prolongation of the QTc interval, and ST segment depression. The clinical relevance of these findings is unknown.
	Healthy participants are included who will be carefully screened against the defined inclusion and exclusion criteria (including overall cardiac health, vital signs, ECG interval values, and lab safety values [including serum potassium and glucose levels] and by ECG monitoring and lab PD/safety assessments (including serum potassium and glucose levels) as per Section 1.3.
Study Procedures		
There are no risks associated with the study design and/or procedures.		

2.3.2. Benefit Assessment

- The healthy participants will receive medical assessments associated with study procedures, for example, physical examination, ECG and labs. They may, as a result, derive some benefit related to information about their general health status.
- The healthy participants will be contributing to the understanding of PK and PD for all MDI-based therapies with salbutamol and HFA-152a. The healthy participants will be contributing to the process of developing a therapy which has a reduced impact on global warming.

2.3.3. Overall Benefit Risk Conclusion

Taking into account the measures taken to minimize risk to participants participating in this study, the potential risks identified in association with salbutamol administered via MDI containing propellants HFA-152a and HFA-134a are justified by the anticipated benefits to all ongoing and future programs with HFA-152a as a propellant as well as the anticipated environmental and societal benefits of introducing a new propellant (HFA-152a) with greatly reduced GWP compared to the current propellant HFA-134a.

3. OBJECTIVES, ENDPOINTS AND ESTIMANDS

Table 3 Objectives and Endpoints

Objective(s)	Endpoint(s)
Primary	
To characterize the PK of single doses of salbutamol in healthy participants delivered via an MDI containing propellant HFA-152a (test), and to compare with an MDI containing propellant HFA-134a (reference) in the following cohorts: Cohort 1: Salbutamol HFA-152a MDI 200 µg (test), HFA-134a MDI 200 µg (reference) Cohort 2: Salbutamol HFA-152a MDI 800 µg (test), HFA-134a MDI 800 µg (reference)	
 • AUC(0-30min) • AUC(0-∞) • Cmax
Secondary	
Pharmacokinetic: To characterize the PK of single doses of salbutamol in healthy participants delivered via an MDI containing propellant HFA-152a (test), and to compare with an MDI containing propellant HFA-134a (reference) in the following cohorts: Cohort 1: Salbutamol HFA-152a MDI 200 µg (test), HFA-134a MDI 200 µg (reference) Cohort 2: Salbutamol HFA-152a MDI 800 µg (test), HFA-134a MDI 800 µg (reference)	Pharmacokinetic: 
 • Tmax • t1/2 • AUC(0-last)

Pharmacokinetics: To measure the intra-participant variability in PK of single doses of salbutamol for healthy participants delivered via an MDI containing propellant in the following cohorts:
 
Cohort 1: Salbutamol HFA-152a MDI 200 µg (test), Salbutamol HFA-134a MDI 200 µg (reference)
 
Cohort 2: Salbutamol HFA-152a MDI 800 µg (test), Salbutamol HFA-134a MDI 800 µg (reference)
	
Pharmacokinetics:
 
 • Intra-participant variability of AUC(0-30min), AUC(0-∞), AUC(0-last), and Cmax of HFA-152a (test) • Intra-participant variability CVw of AUC(0-30min), AUC(0-∞), AUC(0-last), and Cmax of HFA-134a (reference)

Safety: To assess the safety and tolerability of single doses of salbutamol in healthy participants delivered via MDI HFA-152a (test) or propellant HFA-134a (reference) in the following cohorts:
 
Cohort 1: Salbutamol HFA-152a MDI 200 µg (test), HFA-134a MDI 200 µg (reference)
 
Cohort 2: Salbutamol HFA-152a MDI 800 µg (test), HFA-134a MDI 800 µg (reference)
	
Safety:
 
 • Incidence of AEs and SAEs • Absolute values for 12 lead ECGs recording of HR and QTc intervals at each assessed visit • Change from baseline for postdose 12 • lead ECGs recording of HR and QTc intervals at each assessed visit • Absolute values of clinical laboratory parameters at each assessed visit • Absolute values of vital signs (systolic and diastolic blood pressure and pulse rate) at each assessed visit
Exploratory	

Pharmacodynamics: To characterize the PD of single doses of salbutamol in healthy participants delivered via an MDI containing propellant HFA-152a (test), and to compare to an MDI containing propellant HFA-134a (reference) in the following cohorts:
 
Cohort 1: Salbutamol HFA-152a MDI 200 µg (test), Salbutamol HFA-134a MDI 200 µg (reference)
 
Cohort 2: Salbutamol HFA-152a MDI 800 µg (test), Salbutamol HFA-134a MDI 800 µg (reference)
	
Pharmacodynamics:
 
 • Minimum serum potassium • MHR • Maximum QTc interval

3.1. Primary Estimands

Cohort 1:

Test: Salbutamol HFA-152a MDI 200 µg

Reference: Salbutamol HFA-134a MDI 200 µg

The primary clinical question of interest for Cohort 1 is-

What is the GMR for Cohort 1 in primary PK parameters (AUC(0-30min), AUC(0-∞) and Cmax) of salbutamol HFA-152a and salbutamol HFA-134a in healthy participants after administration of single dose of 200 μg?

The primary estimand for Cohort 1 is described by the following attributes:

- The population is healthy male or female participants aged 18 to 55 years.
- The primary PK parameters endpoints are AUC(0-30min), AUC(0-∞) and Cmax.
- Treatment condition is administration of salbutamol as a single 200 μg dose, given as 2 actuations each separated by a 20-second interval, each delivering 100 μg of salbutamol (as salbutamol sulfate) as the ex-valve dose for the HFA-152a MDI or HFA-134a MDI.
- The ICEs and estimand strategies are as follows:
 - Study treatment discontinuation due to any reason (hypothetical strategy).
 - Occurrence of emesis or coughing on dosing (hypothetical strategy).
 - Dosing error: Considered less than or more than prescribed dose (hypothetical strategy).
 - Use of prohibited or rescue medication which impacts to PK parameters (hypothetical strategy).

For all ICEs, interest lies in evaluating the primary PK parameters and comparisons of the ratio of 2 formulations for each primary PK parameters in a hypothetical scenario in which the participant had not experienced an intercurrent event. This is to minimize potential confounding of ICEs on individual PK parameters across treatment periods.

- The population-level summary to be estimated is:

Ratio of adjusted GM (for logarithmic transformed values) of 2 formulations with 90% CI for each primary PK endpoint.

Cohort 2:

Test: Salbutamol HFA-152a MDI 800 μg

Reference: Salbutamol HFA-134a MDI 800 μg

The primary clinical question of interest for Cohort 2 is –

What is the GMR for Cohort 2 in primary PK parameters (AUC(0-30min), AUC(0-∞) and Cmax) of salbutamol HFA-152a and salbutamol HFA-134a in healthy participants after administration of single dose of 800 μg?

The estimand for Cohort 2 has the same estimand attributes as Cohort 1 (population, PK endpoints, population-level summary measure, ICE strategy), except for the attribute for the treatment condition:

- Treatment condition is administration of salbutamol as a single 800 µg dose, given as 8 actuations each separated by a 20-second interval, each delivering 800 µg of salbutamol (as salbutamol sulfate) as the ex-valve dose for the HFA-152a MDI or HFA-134a MDI.

Rationale for primary estimands for both cohorts: The test formulation is being developed with an aim to have comparable PK characteristics as the reference formulation. Interest lies in the PK values obtained in the scenarios that had the participant been exposed to correct dose as prescribed, where study treatment discontinuation of the randomized sequence, the occurrence of emesis or coughing on dosing, and prohibited rescue medication usage had not occurred.

3.2. Estimands supporting secondary PK objectives

3.2.1. PK Parameters

Cohort 1:

Test: Salbutamol HFA-152a MDI 200 µg

Reference: Salbutamol HFA-134a MDI 200 µg

The secondary clinical question of interest for Cohort 1 is:

What is the summarized PK profile in Cohort 1 using descriptive statistics for Tmax and t_{1/2} and GMR for AUC(0-last) between salbutamol HFA-152a and salbutamol HFA-134a in healthy participants after administration of single dose of 200 µg?

The secondary estimand for Cohort 1 has the same estimand attributes as the primary estimand for Cohort 1 (population, treatment condition, ICE strategy), except for the estimand attributes of PK endpoints and population-level summary measure:

- The secondary PK parameters endpoints are Tmax, t_{1/2}, AUC(0-last).
- The population-level summary to be estimated are:
 - AM with 95% CI for Tmax and GM with 95% CI for t_{1/2}.
 - Ratio of adjusted GM (for logarithmic transformed values) of 2 formulations with 90% CI AUC(0-last).

Cohort 2:

Test: Salbutamol HFA-152a MDI 800 µg

Reference: Salbutamol HFA-134a MDI 800 µg

The secondary clinical question of interest for Cohort 2 is –

What is the summarized PK profile in Cohort 2 using descriptive statistics for Tmax and t1/2 and GMR for AUC(0-last) between salbutamol HFA-152a and salbutamol HFA-134a in healthy participants after administration of single dose of 800 μg ?

The secondary estimand for Cohort 2 has the same estimand attributes as the primary estimand for Cohort 2 (population, treatment condition, ICE strategy), except for the estimand attributes of PK endpoints and population-level summary measure:

- The secondary PK parameters endpoints are Tmax, t1/2, AUC(0-last).
- The population-level summary to be estimated are:
 - AM with 95% CI for Tmax and GM with 95% CI for t1/2.
 - Ratio of adjusted GM (for logarithmic transformed values) of 2 formulations with 90% CI AUC(0-last).

3.2.2. Intra-participant variability of PK Parameters

Cohort 1:

Test: Salbutamol HFA-152a 200 μg

Reference: Salbutamol HFA-134a 200 μg

The secondary clinical question of interest for Cohort 1 is –

What is the intra-participant variability of the PK profile of Cohort 1 using CVw for AUC(0-30min), AUC(0- ∞), Cmax and AUC(0-last) PK parameters for salbutamol HFA-152a and salbutamol HFA-134a in healthy participants after administration of single dose of 200 μg ? This secondary objective is to establish whether either the reference or test product is considered a high variable product at the 200 μg dose level (CVw > 30%).

The secondary estimand for Cohort 1 has the same estimand attributes as the primary estimand for Cohort 1 (population, treatment condition, ICE strategy), except for the estimand attributes of PK endpoints and population-level summary measure:

- The secondary PK parameters endpoints for HFA-152a (test) and HFA-134a (reference) are:
 - Intra-participants variability in AUC(0-30min)
 - Intra-participants variability in AUC(0- ∞)
 - Intra-participants variability in Cmax
 - Intra-participants variability in AUC(0-last)

- The population-level summary to be estimated for HFA-152a (test) and HFA-134a (reference) are:
 - Intra(within)- participants CVw (%) for AUC(0-30min), AUC(0-∞), Cmax and AUC(0-last)

Cohort 2:

Test: Salbutamol HFA-152a 800 µg

Reference: Salbutamol HFA-134a 800 µg

The secondary clinical question of interest for Cohort 2 is –

What is the intra-participant variability in PK profile of Cohort 2 using CVw for AUC(0-30min), AUC(0-∞), Cmax and AUC(0-last) PK parameters for salbutamol HFA-152a and salbutamol HFA-134a in healthy participants after administration of single dose of 800 µg?. This secondary objective is to establish whether either the reference or test product is considered a high variable product at the 800 µg dose level (CVw > 30%).

The secondary estimand for Cohort 2 has the same estimand attributes as the primary estimand for Cohort 2 (population, treatment condition, ICE strategy), except for the estimand attributes of PK endpoints and population-level summary measure:

- The secondary PK parameters endpoints for HFA-152a (test) and HFA-134a (reference) are:
 - Intra-participants variability in AUC(0-30min)
 - Intra-participants variability in AUC(0-∞)
 - Intra-participants variability in Cmax
 - Intra-participants variability in AUC(0-last)
- The population-level summary to be estimated for HFA-152a (test) and HFA-134a (reference) are:
 - Intra(within)- participants CVw (%) for AUC(0-30min), AUC(0-∞), Cmax and AUC(0-last)

Rationale for supporting secondary estimands of PK parameters for both cohorts:
Rational for supporting secondary estimands of PK parameters for both cohorts is same as primary estimands.

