9.1. Statistical hypotheses

This study is designed to estimate the relative bioavailability of salbutamol HFA-152a (test) and Salbutamol HFA-134a (reference) in following cohorts:

Cohort 1: Salbutamol HFA-152a 200 µg, Salbutamol HFA-134a 200 µg.

Cohort 2: Salbutamol HFA-152a 800 µg, Salbutamol HFA-134a 800 µg.

In each cohort, for each PK parameters endpoints (AUC(0-30min.), AUC(0-∞), Cmax and AUC(0-last)), point estimates and corresponding 90% CIs will be constructed for GMR(T/R).

90% Confidence Interval of GMR (T/R): The GMR is calculated by taking the ratio of the geometric means of the salbutamol HFA-152a (T) to the salbutamol HFA-134a (R). The 90% confidence interval of this GMR is a range that provides a measure of the uncertainty in this ratio.

An additional assessment will be performed by comparing the 90% CIs for the GMR(T/R) in AUC(0-30min), AUC(0-∞), Cmax and AUC(0-last) PK parameters to the bioequivalence acceptance range (refer to Section 10.8, [Table 12](#)).

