9.5. Sample size determination

Up to 60 healthy participants will be enrolled to either Cohort 1 (200 µg) or Cohort 2 (800 µg) to achieve at least 56 participants in the PK analysis set.

For each cohort, 30 healthy participants will be randomly assigned to a cohort to ensure at least 28 participants are included in the PK analysis set with 15 randomized to each treatment sequence.

The target number of participants in each cohort is chosen to achieve half width (refer [Table 9](#)) of the 90% CI, in the estimate of the geometric mean ratios for the primary endpoints (AUC (0-30 min.), AUC(0-inf) and Cmax).

In the previously conducted 219430 pilot PK study, there was considerable interest in AUC(0-30 min) due to larger than expected observed differences between test and reference product, in addition to observing potentially higher amounts of intra-subject variability that would classify the product as highly variable (~30%). Though, less variability was observed among AUC(0-inf) and Cmax. Due to uncertainty of what the true CVw may be for both the reference and test products, this current study therefore has considered a more conservative assumption accounting for up to 50% intra subject variability (CVw) in PK parameters, with a particular interest in AUC(0-30 min).

Therefore, a sample size 28 in each cohort, assuming intra subject variability (CVw) of 50% in AUC(0-30 min.), the half width of the upper bound of the 90% CI for observed GMR (T/R) is 16.44% (refer [Table 9](#)).

For example, if the geometric ratio between test and reference is 1.06 for n=28 and CVw = 50%, then the upper bound of the 90% CI for observed treatment ratio is $1.06 * (1 + 0.1644) = 1.23$ and the lower bound is $1.06 / (1 + 0.1644) = 0.91$ (refer [Table 10](#)).

Table 9 Sample sizes with varying intra subject variability and associated half-widths of the 90% CI of the observed treatment ratio

CCI

CCI

Table 10 Sensitivity Table

CCI

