**Estimand for Intra-participant variability of pharmacokinetic (PK) parameters**

Cohort 1:

Test: Salbutamol HFA-152a 200  $\mu\text{g}$

Reference: Salbutamol HFA-134a 200  $\mu\text{g}$

The secondary clinical question of interest for Cohort 1 is -

What is the intra-participant variability of the PK profile of Cohort 1 using  $CV_{WR}$  for AUC (0-30min), AUC (0- $\infty$ ), Cmax and AUC (0-last) PK parameters for salbutamol HFA-152a and salbutamol HFA-134a in healthy participants after administration of a single dose of 200  $\mu$ g?

This secondary objective is to establish whether either the reference or test product is considered a high variable product at the 200  $\mu$ g dose level ( $CV_{WR}>30\%$ ).

The secondary estimand for Cohort 1 has the same estimand attributes as the primary estimand for Cohort 1 (population, treatment condition, ICE strategy), except for the estimand attributes of PK endpoints and population-level summary measure:

- The secondary PK parameters endpoints for HFA-152a (test) and HFA-134a (reference) are:
  - Intra-participants variability in AUC(0-30min)
  - Intra-participants variability in AUC(0- $\infty$ )
  - Intra-participants variability in Cmax
  - Intra-participants variability in AUC(0-last)
- The population level summaries to be estimated for HFA-152a (test) and HFA-134a (reference) are:
  - Intra(within)- participants  $CV_{WR}$  (%) for AUC(0-30min), AUC(0- $\infty$ ), Cmax and AUC(0-last)

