##### Statistical model for estimating the intra-participants (with-in) variability for PK parameters – AUC (0-30min), AUC (0-∞), Cmax and AUC (0-last)

For each cohort, following  $\log_e$ -transformation, AUC (0-30min.), AUC (0-∞), Cmax and AUC (0-last) will be analyzed using a mixed effect model approach with fixed for period, treatment group and participants as random effects. Factor Analytic (FA(02)) variance and covariance structures will be assumed. If the above model fails to converge, other covariance structures (e.g. UN, CS, AR (1), VC etc.) might be investigated. SD in  $\log_e$  scale and coefficient of variation (CVWR) for intra (within)-participants will be computed, where  $\%CV_{WR}=100*(\text{SQRT } (\text{EXP}(\sigma_{WR}^2)-1))$  and  $\sigma_{WR}^2$  is the mean squares error (MSE) or residual in  $\log_e$  scale from the statistical mixed model.

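### The plan sets out to establish whether each product's within-participant CV exceeds 30%, but reports CVw without an interval, and estimates between about 23% and 37% cannot settle the question

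*Protocol*

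**What the plan says.** Protocol 3.2.2 gives the purpose of the variability objective: "This secondary objective is to establish whether either the reference or test product is considered a high variable product at the 200 μg dose level". The criterion is CVw above 30%, and the sentence recurs for Cohort 2 at 800 µg. SAP 4.3.1.1 carries it over: "This secondary objective is to establish whether either the reference or test product is considered a high variable product at the 200" (µg dose level).

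The population-level summary in Protocol 3.2.2 is "Intra(within)- participants CVw (%) for AUC(0-30min), AUC(0-∞), Cmax and AUC(0-last"), for test and for reference, with no interval. In the SAP's model section for within-participant variability (4.3.1.2), the log-scale SD and the "coefficient of variation (CV WR ) for intra (within)-participants will be computed" from the mean square error or residual of a mixed model. No interval is mentioned there either.

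The neighbouring PK estimands do carry intervals. Protocol 3.2.1 gives 95% intervals for Tmax and t1/2 and a 90% interval for the AUC(0-last) ratio. For the ratios generally, Protocol 9.1 says "point estimates and corresponding 90% CIs will be constructed for GMR(T/R").

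Protocol 9.5 sizes the trial on the width of the ratio's interval, with 30 participants per cohort "randomly assigned to a cohort to ensure at least 28 participants are included in the PK analysis set". The same section describes the pilot, in its discussion of AUC(0-30min), as showing "potentially higher amounts of intra-subject variability that would classify the product as highly variable (~30" per cent). It adds that AUC(0-∞) and Cmax were less variable, and it plans for a CVw of up to 50%.

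**The concern.** To *establish* that a product lies above or below a cut-off is a stronger claim than to estimate its variability. A variance estimated from two replicates per product in 28 people is imprecise, and the planned output would not show how imprecise. A reader of the report would see, say, 33% or 27% and could take the question as answered when the data are compatible with either side of 30%. This is the PK objective worded as a classification, and it is also the one whose summary has no measure of precision.

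**Working it through.** **The plan's own figure.** For n = 28 and CVw = 50%, Protocol 9.5 states a half-width of 16.44% for the ratio.
- σw = √ln(1 + 0.50²) = 0.4724, and SE = 0.4724/√28 = 0.0893.
- With t(0.95; 26) = 1.7056, exp(1.7056 × 0.08927) − 1 = 16.45%, which agrees up to rounding.

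This concerns the ratio only. The visible text gives no precision figure for CVw.

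**Inputs for CVw.**
- 28 participants per cohort (Protocol 9.5).
- Two sequences, TRRT and RTTR, so two test and two reference periods each (Protocol 4.1).
- Cut-off 30% (Protocol 3.2.2).
- Assumptions: log-normal data, complete periods, and a within-participant variance estimated separately for each product. Degrees of freedom are then 28 − 2 = 26.

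**Interval at an observed 30%.** s² = ln(1 + 0.30²) = 0.08618. The 5% and 95% points of chi-square on 26 df are 15.379 and 38.885.
- Lower limit: 26 × 0.08618/38.885 = 0.0576, and √(exp(0.0576) − 1) = 24.4%.
- Upper limit: 26 × 0.08618/15.379 = 0.1457, and √(exp(0.1457) − 1) = 39.6%.

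**Observed values whose 90% interval includes 30%.**
- The upper limit equals 30% at s² = 0.08618 × 15.379/26 = 0.0510, an observed CVw of 22.9%.
- The lower limit equals 30% at s² = 0.08618 × 38.885/26 = 0.1289, an observed CVw of 37.1%.

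**Chance that the estimate falls on the wrong side.** P(observed CVw > 30%) = P(χ²₂₆ > 26 × ln(1.09)/ln(1 + CV²)), where CV is the true value. The documents do not give the true value, so a range is shown.

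| True CVw | 26 × ln(1.09)/ln(1 + CV²) | P(observed > 30%) | Wrong side |
|---|---|---|---|
| 20% | 57.1 | <0.1% | <0.1% |
| 25% | 36.96 | 7.5% | 7.5% |
| 28% | 29.69 | 28% | 28% |
| 32% | 22.98 | 63% | 37% |
| 35% | 19.39 | 82% | 18% |
| 40% | 15.10 | 96% | 4% |
| 50% | 10.04 | 99.8% | 0.2% |

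At a true value of exactly 30% the probability is 46%.

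**Dependence on the model.** SAP 4.3.1.2 describes one residual from a model containing both treatments and uses the reference label (CV_WR) for both products. A single pooled residual would have about 3 × 28 − 4 = 80 df. The interval at an observed 30% would then be 26.5% to 34.8%, but it would describe neither product separately, and the objective asks about each. The next SAP model has a heading that mentions test and reference, but its stated output is inter-participant variability.

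**The case against.** The strongest reply is that the objective is really estimation. Protocol Table 3 says the aim is to measure within-participant variability, the clinical question in 3.2.2 asks what it is, and SAP 4.1 says no formal hypothesis is tested. The plan also classifies on the observed value elsewhere: Protocol 4.2 and 9.3.1.2 choose between average and reference-scaled bioequivalence from the observed reference variability, and a point estimate is enough for that rule. This largely stands. It makes the problem one of wording and reporting, not of design. It does not remove the sentence about establishing a property, it does not cover the test product, and estimation also calls for an interval.

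Three stronger readings are tempting, and the documents do not support them.
- **That the classification is a coin toss because n is 28.** A near-even split occurs when the true value sits on the cut-off, whatever the sample size: 46% with 26 df, 48% with 80 and 49% with 998. What n = 28 determines is the width of the unresolved zone. The 30% in Protocol 9.5 may be the pilot estimate or the threshold for a highly variable product, no product or dose is named, and it belongs to the AUC(0-30min) discussion.
- **That there will be 16 verdicts** (four parameters, two products, two doses). The text asks about a product at a dose level and sets no verdict per parameter.
- **That a chance difference in CVw between propellants or doses will be reported as real.** No section plans such a comparison.

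Parts of both documents are blacked out, including the standard-error and reference-scaling appendices. The absence of an interval can be claimed only for the visible text, although that includes the estimand and model sections where one would be expected.

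**Conclusion.** The point holds as a mismatch between an objective worded as establishing a property and a summary that gives no precision. For a true CVw of roughly 28% to 35%, the point estimate falls on the wrong side of 30% in about 18% of cases or more. At 25% or below the chance is 7.5% or less, and at the 50% planning value it is 0.2%. The exposure is mainly in AUC(0-30min). For AUC(0-∞) and Cmax the pilot was less variable, though no figures are given, and nothing is said about AUC(0-last). The sizes rest on 26 df per product, complete data and log-normality. Missing periods would widen the intervals. The primary ratio analysis, the sample size and the bioequivalence switch are not affected. This is an inexpensive improvement to one secondary summary.

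**What to change.** In Protocol 3.2.2 and SAP 4.3.1.1, change the summary to CVw (%) with a 90% confidence interval, and replace the wording about establishing whether a product is highly variable with estimating CVw, with its interval, relative to 30%. In SAP 4.3.1.2, state that the within-participant variance is estimated separately for test and reference, and name the interval method (for example, chi-square limits on the log-scale variance).

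Leave the observed-value rule for average or reference-scaled bioequivalence unchanged. Do not add a formal yes / no / not-established rule. At 26 df it would return *not established* in about 70% of cases at a true 25%, 90% at 30% and 68% at 35%. It would also sit awkwardly beside the switch: an observed reference CVw of 33% would trigger reference scaling and yet be labelled *not established*.

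The cost is SAP wording and one extra table column. The downside is that the interval will often include 30% when the true CVw is about 25% to 35%, which is a fair account of what the data can show.
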